## 1. Abstract

Sponsor Identification	Instituto de Investigación Sanitaria Puerta de Hierro [name]
Study Title	Project to enhance Dermatology E-Consultations in Primary Care Centres using Artificial Intelligence Tools.
Protocol code	LEGIT.HEALTH_DAO_Derivación_PH_2022
Protocol version and date	Version: 1.0. Date: 29/06/2022
Research Coordinator	[name] [name] Dermatology Service Puerta de Hierro Majadahonda University Hospital [name]
Principal Investigator	[name] [name] Dermatology Service Puerta de Hierro Majadahonda University Hospital [name]
Collaborating investigators	[name] Majadahonda Health Center [name] Pozuelo Health Center [name] Dermatology Service

	Puerta de Hierro Majadahonda University Hospital
Investigational centers	Puerta de Hierro Majadahonda University Hospital Majadahonda Health Center Pozuelo Health Center
Ethics Committee	Research Ethics Committee of the Puerta de Hierro Majadahonda University Hospital
Primary Objective	The main objective of this study is to validate the clinical utility of the Legit.Health platform developed by AI LABS GROUP SL in the management of patients with skin pathology by primary care physicians and dermatologists of the Puerta de Hierro Majadahonda University Hospital involved in the project.
Design	Prospective observational analytical study of a series of clinical cases with a longitudinal character.
Disease under study	Patients suspected of having the following pathologies in Primary Care: tumor pathology, inflammatory pathology, and infectious pathology
Study Population and Total Number of Subjects	100 adult patients attending their primary care center with tumor pathology, inflammatory pathology, or infectious pathology.
Calendar. Planned Duration of the Study	The study will last 5 months, with 4 months of recruitment time and 1 month for data analysis.
Ethical Considerations	The development of the study will comply with international Good Clinical Practice (GCP) guidelines, the Declaration of Helsinki in its latest active amendment, and applicable international

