## 4. Methods

### Study design

This is a prospective, observational, analytical study of a series of clinical cases.

It is a longitudinal study.

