**Variables**

The main variable aims to determine the clinical utility of the platform developed by AI LABS GROUP SL in the management of patients with skin pathology by primary care physicians and dermatologists of the Puerta de Hierro Majadahonda University Hospital involved in the project.

For this purpose, clinicians will complete the **Clinical Utility and Satisfaction Questionnaire (Annex I)**.

In addition, the following secondary variables will be collected::

- Patient demographics:
  - Sex
  - Age
- Teleconsultation data:
  - Response time
  - Response label (follow-up in primary care, shared follow-up, dermatology follow-up, insufficient or inadequate information)
- Data from the in-person consultation:

- Duration of an in-person dermatology appointment to respond to an online primary care consultation.
- Waiting time until being seen in a specialized dermatology clinic.
- Diagnosis
  - Diagnostic correlation between primary care and dermatology.
  - Number of patients referred by pathology.
  - Diagnostic correlation between primary care, dermatology, and dermatopathology (if applicable).
  - Time elapsed between the day of the primary care visit and the day of the histopathological diagnosis (if applicable).
- Primary care physician satisfaction using the Clinical Utility and Satisfaction Questionnaire (Appendix I).
- Dermatologists satisfaction using the Clinical Utility and Satisfaction Questionnaire (Appendix I).

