## **Procedures to be performed by the primary care physician**

### **1. Consultation**

Primary care physicians will need to take photographs showing the areas affected by the condition. These photographs will be taken with their own smartphone or using a mobile dermatoscope if its use is clinically relevant. Primary care physicians will upload the photographs to the Legit.Health platform.

Primary care physicians will assess the patient's condition through direct observation and guided by the results from the platform. They will enter the diagnosis into the Legit.Health platform by selecting the condition if it is among the first 5 or by using a drop-down menu that displays a wide range of conditions.

In addition to the most likely diagnoses, physicians will have access to referral criteria, the clinical referral questionnaire, and basic treatment advice. When they deem it necessary, they will refer the patient in their Selene system, as they normally would; not through Legit.Health.

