## 11. Annexes

### Annex I - Clinical Utility and Satisfaction Questionnaire

Based on their experience, without needing to consult the Medical History:

1. Average weekly number of patients with skin conditions you have seen in your practice during the last two months (approximate).
2. Name the conditions for which Legit.Health has been most useful in your daily clinical practice.
3. In your opinion, indicate the impact of Legit.Health from 0 to 10 (where 0 is “no impact” and 10 is “great impact”) on the accuracy of your diagnostic decisions for each of the following diseases:
  - a. Urticaria
  - b. Psoriasis
  - c. Hidradenitis Suppurativa
  - d. Melanoma
  - e. Atopic Dermatitis
  - f. Other (add any other diseases where the tool has had an impact at this point and rate the impact from 0 to 10)
4. In your opinion, please indicate the impact of Legit.Health from 0 to 10 (where 0 is “no impact” and 10 is “great impact”) in relation to reducing the time to issue your diagnostic decision for each of the following diseases:
  - a. Urticaria
  - b. Psoriasis
  - c. Hidradenitis Suppurativa
  - d. Melanoma
  - e. Atopic Dermatitis
  - f. Other (add any other conditions where the tool has had an impact at this point)
5. In your opinion, please indicate the impact of Legit.Health from 0 to 10 (where 0 is “no impact” and 10 is “great impact”) on your therapeutic decision-making, thanks to the included management recommendations, for each of the following diseases:
  - a. Urticaria
  - b. Psoriasis
  - c. Hidradenitis Suppurativa

- 
- d. Melanoma
  - e. Atopic Dermatitis
  - f. Other (add any other conditions where the tool has had an impact at this point)
6. In your opinion, please indicate the impact of Legit.Health from 0 to 10 (where 0 is “no impact” and 10 is “great impact”) on monitoring the evolution of skin lesions for each of the following diseases:
- a. Urticaria
  - b. Psoriasis
  - c. Hidradenitis Suppurativa
  - d. Melanoma
  - e. Atopic Dermatitis
  - f. Other (add any other conditions where the tool has had an impact at this point)
7. In your opinion, please indicate the impact of Legit.Health from 0 to 10 (where 0 is “no impact” and 10 is “high impact”) on the efficiency of interconsultations/referrals to the dermatology service (in cases where referral applies) for each of the following diseases:
- a. Urticaria
  - b. Psoriasis
  - c. Hidradenitis Suppurativa
  - d. Melanoma
  - e. Atopic Dermatitis

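### Annex I item 6 asks for the tool's impact on monitoring lesion evolution, but no repeat imaging is planned and a clinician who never used it that way has no answer except a 0-10 score

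*Combined protocol and SAP*

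**What the plan says.** Section 4 (Variables) makes the Annex I questionnaire the means of measuring the main variable, clinical utility. Section 5 has primary care physicians and dermatologists complete it at 2 and 4 months.

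Item 6 of Annex I asks for a 0-10 impact "on monitoring the evolution of skin lesions for each of the following diseases": urticaria, psoriasis, hidradenitis suppurativa, melanoma and atopic dermatitis, plus a free line for others. Zero is labelled as absence of impact. There is no option for a function that was not used.

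Section 4 (Study design) states: "It is a longitudinal study". In section 5, the primary care procedure is a consultation at which photographs are taken, and "Primary care physicians will upload the photographs to the Legit.Health platform". The specialist procedure is a visit under standard routine at which the appropriateness of the referral and the diagnoses are recorded. The calendar in section 1 reads: "The study will last 5 months, with 4 months of recruitment time and 1 month for data analysis".

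**The concern.** Rating how well a tool helps to follow a lesion over time presupposes that the rater has used it on the same lesion at least twice. The protocol describes no step that would bring this about. The difficulty differs from that of a physician who has seen few cases of a disease: here the function has no planned use, however often the disease is seen.

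An item 6 rating may therefore reflect real repeat use, a guess about an untried function, or a zero meaning that it was never tried. The form records all three in the same way. Section 7 foresees presenting the survey results at scientific meetings and in press releases, so monitoring ratings with no experience behind them could be reported beside ratings that do have it.

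**Working it through.** **1. Is there planned exposure for each disease-specific item?** The section 5 consultation procedure lists what the physician receives from the platform: likely diagnoses, criteria for referral, a referral questionnaire and basic advice on treatment. Set against the five items:

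| Annex I item | Construct | Matching output in section 5 |
|---|---|---|
| 3 | "on the accuracy of your diagnostic decisions for each of the following diseases" | likely diagnoses |
| 4 | "in relation to reducing the time to issue your diagnostic decision for each of the following diseases" | likely diagnoses |
| 5 | "on your therapeutic decision-making, thanks to the included management recommendations, for each of the following diseases" | treatment advice |
| 6 | "on monitoring the evolution of skin lesions for each of the following diseases" | none listed |
| 7 | efficiency of referrals to dermatology | referral criteria and questionnaire |

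Four of the five items have a counterpart. Item 6 has none. No section 4 variable measures change in a lesion, and no section 5 procedure gives a repeat image set, return visit or interval. Dermatologists complete the same form, but their procedure describes no use of the tool.

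**2. Does the timetable create exposure?** Recruitment takes 4 months and analysis follows in the fifth. The last questionnaire falls at month 4, when recruitment ends. A patient enrolled early could return before then; one enrolled late has almost no time to do so. No separate follow-up period is given.

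**3. Can an unexposed rating be recognised?** Item 7 is restricted in its wording to cases where a referral is relevant. Item 6 carries no such restriction and no not-used response.

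**4. How large is item 6?** The plan states no share or score for it, so there is no figure of its own to reproduce. Counting from Annex I:

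- Fixed disease ratings: items 3 to 7 × 5 diseases = 25. Item 6: 5/25 = 20.0%.
- With the free lines for other diseases: 6/30 = 20.0%.
- With item 8 (overall satisfaction) added to the 25: 5/26 = 19.2%.
- With item 8 and perceived patient satisfaction: 5/27 = 18.5%.
- With the free lines and both satisfaction ratings: 6/32 = 18.8%.

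Over two administrations, each clinician gives 2 × 25 = 50 fixed disease ratings, of which 2 × 5 = 10 come from item 6. Without item 6, 40 remain.

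**5. Illustration only.** Assume an unweighted mean of the 25 ratings, a common average m on the other 20, and item 6 scored 0 throughout because the function was not used. The mean is then 20m/25 and the drop is m/5.

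- m = 5: 100/25 = 4.0, a drop of 1.0.
- m = 7: 140/25 = 5.6, a drop of 1.4.
- m = 8: 160/25 = 6.4, a drop of 1.6.

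If item 6 is instead guessed at m, the drop is 0. Neither the unweighted mean nor any value of m comes from the protocol.

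**The case against.** The strongest reply is that the protocol leaves room for monitoring. It calls itself longitudinal, three of its four teleconsultation response labels foresee some form of follow-up, and care follows usual practice. A patient could be photographed again within the four months. Annex I also asks for opinion drawn from the clinician's own experience, and section 5 (Patient identification) describes the aim as utility perceived by physicians. Monitoring appears in neither the hypothesis nor the objectives, and the study is a proof-of-concept pilot.

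Much of this stands, and it rules out several stronger readings that a reader might infer:

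- That the design allows one imaging consultation per patient and no follow-up, so that the study never monitors a lesion. The documents schedule no repeat imaging, but they do not exclude it.
- That the clinicians' questionnaire is the only thing tracked over time. Diagnoses are recorded at primary care, dermatology and, where applicable, pathology, as are waiting time and time to histopathological diagnosis.
- That the main result would shift by 1.4 points. This needs a composite that the protocol does not define.
- That the sponsor already plans to claim validated monitoring utility. No section says so.

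The reply does not remove the narrower defect. Incidental repeat use is not recorded anywhere in the plan, and the answer sheet cannot show which raters had it. An appeal to experience helps only if the plan provides the experience or asks whether it occurred.

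**Conclusion.** The point holds in a limited form. Item 6 belongs to the main-variable instrument, has no planned exposure behind it, and cannot separate a function never used from a function used without benefit. It affects 5 of 25 fixed disease ratings (20%), or 5 of 27 (18.5%) with both satisfaction ratings. That share is a count; its influence on any summary is unknown until a scoring rule exists.

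The conclusion assumes that section 5 lists the procedures and tool outputs relevant to this study. If the platform is in fact meant to be used serially, the protocol needs to say so. Even then, clinicians without serial use would need a not-used response. This is a correctable weakness of the questionnaire and does not invalidate the study.

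**What to change.** 1. Before item 6, ask each clinician whether they used the tool on the same lesion on two or more dates, and for about how many patients.
2. Add a not-used response to item 6, and state that it is not scored as 0.
3. Report item 6 descriptively, apart from the other main-variable ratings, only for clinicians who report such use, and give their number.
4. State in section 4 that no repeat patient imaging is planned, and that no conclusion on monitoring utility will be drawn from ratings without such use.

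Self-report is preferable to a count of repeat uploads from the platform. The documents do not say that the platform holds dated image series for the same lesion. The patient identification text in section 5 says that patients' data will not be analysed. An upload count would also exclude dermatologists, for whom no upload step is described.

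The cost is two added questionnaire fields and a written amendment under section 8, best in place before the month 2 questionnaire. No visits or patients are added. The downside is that the sponsor may end with few or no usable monitoring ratings, and that self-reported use relies on recall.
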